#### 11.3.5. Physical and Neurological Examination

Complete PEs as well as neurological exams will be performed. The PE includes an assessment of general appearance and a review of systems (dermatologic, head, eyes, ears, nose, mouth/throat/neck, thyroid, lymph nodes, respiratory, cardiovascular, gastrointestinal, extremities, musculoskeletal, neurologic, and psychiatric systems). The neurological exam includes an assessment of general appearance, mental status, cranial nerves, motor system, sensory system, reflexes, coordination, and gait.

Any clinically significant changes in PE and neuro exam findings from signing of the ICF, as determined by the Investigator, will be noted as AEs in the CRF.

#### 11.3.6. Safety Scales

When applicable, raters will receive training regarding each safety scale prior to performing them.

# 11.3.6.1. Simpson-Angus Scale (SAS)

The SAS is a clinician-rated assessment of neuroleptic-induced Parkinsonism consisting of 10 items. Items are anchor-based, rated on a 5-point scale of severity, and address rigidity, gait (bradykinesia), tremor, akathisia, shoulder shaking, glabellar tap, and salivation (Siddiqui-2009; Simpson-1970). The SAS will be administered by a qualified rater at the site.

#### 11.3.6.2. Barnes Akathisia Rating Scale (BARS)

The BARS is a rating scale geared toward assessment of neuroleptic-induced akathisia, though it can be used to measure akathisia associated with other drugs as well. The BARS consists of four items, including one item assessing objective restlessness, two items targeting subjective restlessness (awareness and related distress), and one global clinical assessment item. All items are anchored and utilize a 4-point scale, except for the global rating which has a 6-point scale (from absence of akathisia through severe akathisia). The subjective and objective items are summed to yield a total score. The BARS can be administered in about 10 minutes (Barnes-1989; Barnes-2003). The BARS will be administered by a qualified rater at the site.

#### 11.3.6.3. Abnormal Involuntary Movement Scale (AIMS)

The AIMS is a clinician-rated assessment of abnormal movements consisting of unobtrusive observation of the subject at rest (with shoes removed) and several questions or instructions directed toward the subject. Using a severity scale ranging from 0 (none) to 4 (severe), clinicians rate dyskinesia in several body regions, including the facial area, extremities, and trunk. There are two items related to dental status, as well as three global impression items assessing overall severity, incapacitation, and the subject's awareness of abnormal movements (Guy-1976; Munetz-1988). The AIMS will be administered by a qualified rater at the site.

#### 11.3.6.4. Columbia Suicide Severity Rating Scale (C-SSRS)

The C-SSRS is a tool designed to systematically assess and track suicidal adverse events (suicidal behavior and suicidal ideation) throughout the trial. The strength of this suicide classification system is in its ability to comprehensively identify suicidal events while limiting the over-identification of suicidal behavior. The scale takes approximately 5 minutes to administer (Posner-2007). The C-SSRS will be administered by a trained rater at the site. Subjects with Type 4 or Type 5 suicidal ideation during the study will be discontinued from the study and referred to a mental health professional. For all visits, the "Since Last Visit" version of the C-SSRS will be used.

If a subject answers "yes" to "Suicidal Ideation" Item 4 (active suicidal ideation with some intent to act, without specific plan) or Item 5 (active suicidal ideation with specific plan and intent) on any post-Baseline C-SSRS assessment, an associated AE must be reported.

# 11.3.6.5. Pittsburgh Sleep Quality Index (PSQI)

The Pittsburgh Sleep Quality Index (PSQI) consists of 19 self-rated questions used to measure the quality and patterns of sleep in adults. It differentiates "poor" from "good" sleep quality by measuring seven areas (components): subjective sleep quality, sleep latency, sleep duration, habitual sleep efficiency, sleep disturbances, use of sleeping medications, and daytime dysfunction over the last month (Buysse-1989). The PSQI will be completed by the subject with oversight from the site.

#### 11.4. Effectiveness Assessments

Raters will receive training regarding each assessment prior to performing assessments.

# 11.4.1. Positive and Negative Syndrome Scale (PANSS)

The PANSS is an interview-based measure of the severity of psychopathology in adults with psychotic disorders. The measure is comprised of 30 items and 3 subscales: the Positive subscale assesses hallucinations, delusions, and related symptoms; the Negative subscale assesses emotional withdrawal, lack of motivation, and similar symptoms; and the General Psychopathology subscale addresses other symptoms such as anxiety, somatic concern, and disorientation. An anchored Likert scale from 1 - 7, where values of 2 and above indicate the presence of progressively more severe symptoms, is used to score each item. Individual items are then summed to determine scores for the 3 subscales, as well as a total score. A Composite scale score (Positive scale score minus Negative scale score) can also be calculated to show the relative valence of positive and negative symptoms. Total time required for the PANSS interview and scoring is approximately 30 to 40 minutes (Kay-1994, Opler-1992; Perkins-2000). The PANSS requires input from an informant (eg, caregiver, relative, friend, case worker, or hospital staff). PANSS interviews will be audio recorded and the recording may be reviewed by Sponsor's designee to monitor the quality of the rater interviews, where allowed by local/regional regulations. No identifying information will be associated with the audio recording. PANSS raters will be required to meet specific training and education criteria before they are certified to rate for this study.

# 11.4.2. Clinical Global Impressions – Severity Scale (CGI-S)

The CGI-S is a clinician-rated assessment of the subject's current illness state on a 7-point scale, where a higher score is associated with greater illness severity. Following a clinical interview, the CGI-S can be completed in 1 to 2 minutes. The CGI-S will be administered by a qualified rater at the site.

# 11.4.3. Clinical Global Impressions – Improvement Scale (CGI-I)

The CGI-I scale is a standard 7-point scale (Guy-1976) that requires the clinician to assess how much the subject's overall symptoms have improved or worsened relative to a baseline state. The CGI-I will be administered by a qualified rater at the site.

#### 11.4.4. Brief Negative Symptom Scale (BNSS)

The BNSS is a rating scale to measure the current level of severity of negative symptoms in schizophrenia and schizoaffective disorder (Kirkpatrick-2011). The measure is comprised of 13 individual items and 6 subscale scores (blunted affect, alogia, avolition, anhedonia, asociality, and distress). The 6 subscale scores provide a summary score and the 13 individual items provide a composite total score (ranging from 0 to 78). Each of the items are scored on a Likert-type 7-point scale from 0 - 6, where values of 0 indicates symptom is absent and a value of 6 means the symptom is a severe form. The number of items varies per subscale. BNSS raters will be required to meet specific training and education criteria before they are certified to rate for this study.

# 11.4.5. 12-Item Short Form Survey (SF-12)

The SF-12 is a 12-item self-reported questionnaire that is a subset of the SF-36 Health Survey. The survey captures physical and mental health. There are 8 subscales including: Physical functioning, Role-physical, Bodily pain, General health, Vitality, Social Functioning, Role emotional, Mental health. The responses are reported on a 3- or 5-point Likert scale, depending on the question. The SF-12 uses 2-items each to estimate scores for 4 of the 8 health concepts (physical functioning, role-physical, role-emotional, and mental health). Score for the remaining 4 healthy concepts (bodily pain, general health, vitality, and social functioning) are estimated using 1 item each. Physical Component Summary (PCS-12) and Mental Component Summary (MCS-12) are computed using the scores of 12 questions and range from 0 to 100, where a zero score indicates the lowest level of health measured by the scales and 100 indicates the highest level of health.

#### 11.4.6. Personal and Social Performance Scale (PSP)

The PSP is a 100-point single-item rating scale of personal and social functioning (Morosini-2000). The rating is based on the assessment of a patient's functioning in four areas: 1) socially useful activities; 2) personal and social relationships; 3) self-care; and 4) disturbing and aggressive behaviors. Higher scores indicate better functioning. Scores of 0 - 30 indicate poor functioning; scores of 31 - 70 indicate varying degrees of difficulty; and scores of 71 - 100 reflect only mild difficulties at most. The PSP will be administered by a qualified rater at the site.

# 11.4.7. Medication Satisfaction Questionnaire (MSQ)

The MSQ is a single-item, patient-rated questionnaire that requires the subject to use a 7-point, Likert-type scale to rate how satisfied they are with their current antipsychotic medication (Vernon-2010). The subject will be asked the following question:

- "Overall, how satisfied are you with your current antipsychotic medication" Subjects will select 1 of 7 potential responses based on their level of satisfaction from (1) extremely dissatisfied to (7) extremely satisfied as follows:
  - (1) Extremely dissatisfied
  - (2) Very dissatisfied
  - (3) Somewhat dissatisfied
  - (4) Neither dissatisfied nor satisfied
  - (5) Somewhat satisfied
  - (6) Very satisfied
  - (7) Extremely satisfied

#### 11.4.8. Healthcare Resource Utilization

Healthcare resource utilization will be assessed by recording the following post Baseline:

- number of physician office visits, ER visits, and hospitalizations (total number and number related to schizophrenia) since prior assessment
- length of each hospital stay since prior assessment
- employment status since prior assessment
- the average number of hours a caregiver(s) spends helping the subject per week (since prior assessment)

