**Table 2: Schedule of Assessments** 

Procedures			Tre	atment Per	iod			Follow-up Period
	V1E	V2E	V3E	V4E	V5E	V6E	V7E	V8E
	OLE Baseline a	Week 4	Week 8	Week 12	Week 16	Week 20	Week 24 EOT/ ET b	Follow-up EOS c
Study Day	Day 1	Day 29 ±3 days	Day 57 ±3 days	Day 85 ±3 days	Day 113 ±3 days	Day 141 ±3 days	Day 169 ±3 days	7±2 days after last dose
Informed consent	X							
Inclusion/exclusion criteria	X							
Concomitant medication review d	X	X	X	X	X	X	X	X
Dispense study drug e	X	X	X	X	X	X		
Study drug accountability		X	X	X	X	X	X	
Telephone contacts f			duled visits					
Physical/neurological examination	Core	X		X			X	X
Nicotine use information	Core			X			X	
Vital signs g	Core	X	X	X	X	X	X	X
Weight (including BMI h)	Core	X	X	X	X	X	X	
Height i	Core Pre- switch screening							
Waist circumference	Core	X		X			X	
12-lead Electrocardiogram (ECG)	Core	X		X			X	
Hematology, chemistry, urinalysis j	Core	X		X			X	
Blood sample for PK k	Core	X		X			X	
Urine drug screen 		X		X			X	
Rapid urine drug screen 	Core							
Serum β-hCG, females only	Core							
Urine β-hCG, females only m		X	X	X	X	X	X	X
Rapid urine β-hCG, females only m	Core							
Positive and Negative Syndrome Scale (PANSS)	Core	X	X		X		X	
Clinical Global Impression – Severity (CGI-S)	Core	X	X		X		X	

**Table 2:** Schedule of Assessments (Continued)

Procedures			Tre	atment Peri	iod			Follow-up Period
	V1E	V2E	V3E	V4E	V5E	V6E	V7E	V8E
	OLE Baseline a	Week 4	Week 8	Week 12	Week 16	Week 20	Week 24 EOT/ ET b	Follow-up EOS c
Study Day	Day 1	Day 29 ±3 days	Day 57 ±3 days	Day 85 ±3 days	Day 113 ±3 days	Day 141 ±3 days	Day 169 ±3 days	7±2 days after last dose
Clinical Global Impression – Improvement (CGI-I)	Core	X	X		X		X	
Brief Negative Symptom Scale (BNSS)	Core	X	X		X		X	
Columbia Suicide Severity Rating Scale (C-SSRS)	Core	X	X	X	X	X	X	X
Simpson-Angus Scale (SAS) n	Core	X					X	
Barnes Akathisia Rating Scale (BARS) n	Core	X					X	
Abnormal Involuntary Movement Scale (AIMS) n	Core	X					X	
Pittsburgh Sleep Quality Index (PSQI)	Core			X			X	
Personal and Social Performance Scale (PSP)	Core			X			X	
Short Form Health Survey (SF-12)	Core						X	
Medication Satisfaction Questionnaire (MSQ)	Core						X	
Healthcare Resource Utilization (HCRU), since last assessment	Pre-switch Baseline visit of Core			X			X	

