Adverse events (AE) monitoring °	X	X	X	X	X	X	X	X

Abbreviations: AE = adverse event; BARS = Barnes Akathisia Rating Scale; β-hCG = human chorionic gonadotropin; BMI = Body Mass Index; BNSS = Brief Negative Symptom Scale; C-SSRS = Columbia Suicide Severity Rating Scale; eCRF = electronic case report form; EDC = electronic data capture; EOS = end of study; EOT = end of treatment; ET = early termination; HCRU = healthcare resource utilization; MSQ = Medication Satisfaction Questionnaire; OLE = open-label extension; PANSS = Positive and Negative Syndrome Scale; PK = pharmacokinetic; PSP = Personal and Social Performance Scale; SAS = Simpson-Angus Scale; SF-12 = Short Form Health Survey.

<sup>a The Week 8 (EOT) visit of Study SEP361-308 serves as the Baseline visit for the present study. "Core" indicates assessments that were conducted at the EOS Visit of Study SEP361-308, unless otherwise indicated, and do not need to be repeated for this study.

<sup>b If a subject discontinues from the study, all ET procedures should be performed at the ET visit, within 48 hours of last study dose.

- c All subjects should have a safety Follow-up Visit 7 (± 2) days after their last dose of study drug. While every effort should be made to complete the Follow-up Visit in the clinic, administration of the C-SSRS, and collection of AEs and concomitant medications may occur by telephone contact if the subject is unable to come to the clinic for the Follow-up Visit.
- d Medications with onset during the Core study (SEP361-308) and ongoing at the start of the current study (SEP361-309) will be entered into the eCRF.
- e All study drug will be taken once daily in the evening at bedtime by mouth, with or without food.
- f Telephone calls will be made by a qualified member of the research staff to the subject **weekly** between scheduled study visits to administer the C-SSRS, collect AEs and concomitant medications, as well as to remind the subject about adherence to study drug administration and upcoming visits.
- g Vital signs will include respiratory rate, oral body temperature and supine and standing measurements of blood pressure and pulse rate.
- h BMI will be derived in the EDC system and during statistical analysis.
- i Height collected at the Core study (SEP361-308) Screening Visit will be re-entered into EDC at Visit 2E of this study.

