## 5.2. Other Objectives

- To evaluate the long-term safety and tolerability of SEP-363856 by assessing:
  - o 12-lead electrocardiograms (ECG)
  - Vital sign measurements
  - Clinical laboratory tests
  - o Columbia Suicide Severity Rating Scale (C-SSRS)
  - o Simpson-Angus Scale (SAS)
  - o Barnes Akathisia Rating Scale (BARS)
  - Abnormal Involuntary Movement Scale (AIMS)
- To evaluate the long-term effectiveness of SEP-363856 using:
  - o Positive and Negative Syndrome Scale (PANSS)
  - o Clinical Global Impression-Severity (CGI-S) scale
  - o Clinical Global Impression-Improvement (CGI-I) scale
  - o Brief Negative Symptom Scale (BNSS)
- To evaluate the long-term effects of SEP-363856 on health-related quality of life as measured by the Short Form Health Survey (SF-12)
- To evaluate the long-term effects of SEP-363856 on functional capacity as measured by the Personal and Social Performance Scale (PSP)
- To evaluate long-term medication satisfaction as measured by the Medication Satisfaction Questionnaire (MSQ)
- To evaluate long-term sleep quality as measured by the Pittsburgh Sleep Quality Index (PSQI)
- To evaluate the long-term impact of SEP-363856 on healthcare resource utilization (HCRU)

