#### 10.3.1. Prohibited Medications

Newly administered psychotropic medications and newly administered medications with a propensity for psychotropic effects are not permitted during the Treatment Period up through the Follow-up Visit, with the exception of the medications discussed in Section 10.3.3. The use of herbal supplements, dietary supplements or other complementary or alternative medications for treating psychiatric indications is not permitted during the Treatment Period; however, is permitted after the last dose of study medication provided, they are not administered prior to the final PANSS assessment.

Use of psychotropic medications after the last dose of study medication is permitted provided, they are not administered prior to the final PANSS assessment.

Subjects who are administered a psychotropic medication (other than the study drug and the acceptable medications described in Section 10.3.3) for the purposes of treating an exacerbation of symptoms associated schizophrenia or due to lack of efficacy of the study treatment will be discontinued from the study.

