# 11.6.9. Visit 8E ( $7 \pm 2$ days after last dose) - Follow-up Period

All subjects who discontinue early or complete the study will have a safety follow-up visit  $7 \pm 2$  days after their last dose of study drug. While every effort should be made to complete the Follow-up Visit in the clinic, administration of the C-SSRS, and collection of AEs and concomitant medications may occur by telephone contact if the subject is unable to come to the clinic for the Follow-up Visit.

The following procedures will be conducted during this visit:

- Concomitant medications
- Physical and neurological examinations
- Vital sign measurements
- Urine sample for β-hCG (for female subjects)
- C-SSRS
- Adverse events

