#### 15.3.5.1. Healthcare Resource Utilization

The number of physician's office visits, ER visits, and hospitalizations (for any reason and those related to schizophrenia) per month at PS Baseline, OLE Baseline, and each scheduled extension visit will be summarized, as well as the average length of hospital stays (for any reason and those related to schizophrenia) at these time points. The frequency and percentage of subjects receiving unpaid care at PS Baseline, OLE Baseline, and each scheduled extension visit, along with the average number of hours a caregiver spends per week helping the subject at these time points, will also be summarized.

The change in the number of physician's office visits, ER visits, and hospitalizations, the average length of hospital stays, and the average number of hours a caregiver spends per week helping the subject from the PS Baseline and from the OLE Baseline at each scheduled extension visit will be summarized. Shifts from the PS Baseline and from the OLE Baseline to each scheduled extension visit in whether the subject receive unpaid care will also be summarized.

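### Healthcare resource use is last recorded at Week 24/ET, so a relapse hospital stay still open at that visit is recorded short and average length of stay is biased downward

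*Protocol*

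**What the plan says.** HCRU is one of the other objectives (Section 5.2) and other endpoints (Section 6.3). Section 11.4.8 collects counts of office visits, ER visits and hospitalizations, together with "length of each hospital stay since prior assessment". Section 15.3.5.1 summarises hospitalizations per month and average length of stay, and also their change from both baselines: "The change in the number of physician's office visits, ER visits, and hospitalizations, the average length of hospital stays".

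The row "Healthcare Resource Utilization (HCRU), since last assessment" in Table 2 is marked, within the extension, only at Week 12 and Week 24/EOT/ET. Sections 11.6.4 and 11.6.7 agree. Section 11.6.9 states that "All subjects who discontinue early or complete the study will have a safety follow-up visit", but its list of procedures contains no HCRU.

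Three rules fix when the last HCRU record is made for a subject who relapses:

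- Section 10.3.1: subjects given a psychotropic that is not allowed "for the purposes of treating an exacerbation of symptoms associated schizophrenia or due to lack of efficacy of the study treatment will be discontinued".
- Section 13.1: stopping study drug means leaving the study.
- Table 2, footnote b: "If a subject discontinues from the study, all ET procedures should be performed at the ET visit, within 48 hours of last study dose". Section 7.1 words the same 48 hours as a target to be met by every effort.

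**The concern.** The event that ends HCRU collection can be the same event HCRU is meant to measure. A subject admitted for relapse and given a non-allowed antipsychotic is discontinued, and the final HCRU assessment then falls due, possibly early in that admission. Only the days accrued so far can be entered as length of stay, and the protocol has no rule for a stay that has not ended. Use between ET and Visit 8E has no HCRU record.

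This truncation depends on outcome: it falls mainly on subjects whose illness worsens. At PS Baseline, subjects were clinically stable outpatients (Section 4.2), so stays reported there would normally have ended. The change in average length of stay would then compare complete stays with cut ones.

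**Working it through.** **Planning figure.** Section 15.1 and the Synopsis give about 67 subjects: 120 × 0.75 × 0.75 = 67.5, which reproduces it. The protocol gives no admission rate and no length of stay, so both are assumptions below.

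**Length of stay.** Let true stays be exponential with mean m, and let recording stop c days after admission. The mean recorded is m(1 − exp(−c/m)). If the last dose is on the admission day and ET is at 48 hours, c = 2. The c = 9 columns show recording on the latest day of the Follow-up window (7 + 2), or equally an ET visit that late.

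| Assumed mean stay (days) | Recorded, c = 2 | Share | Recorded, c = 9 | Share |
|---|---|---|---|---|
| 5 | 1.65 | 33% | 4.17 | 83% |
| 7 | 1.74 | 25% | 5.06 | 72% |
| 10 | 1.81 | 18% | 5.93 | 59% |
| 14 | 1.86 | 13% | 6.64 | 47% |
| 21 | 1.91 | 9% | 7.32 | 35% |

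The exponential form is not critical. A fixed 7-day stay shows 2/7 = 29%, and a fixed 14-day stay 2/14 = 14%.

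**Hospital days per subject.** With an assumed 10% risk of one relapse admission and a 14-day mean stay, the true figure is 0.10 × 14 = 1.40 days and the recorded figure is 0.10 × 1.86 = 0.19 days.

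**Hospitalizations per month.** The admission that leads to discontinuation comes before ET, so it is counted. What changes is the denominator. With intervals starting on Day 1 and a 30.4-day month, an admission on Day 40 with ET on Day 42 gives 30.4/42 = 0.72 per month; followed to Day 85, the same admission gives 30.4/85 = 0.36. The OLE Baseline column of Table 2 points to the pre-switch baseline of the 8-week core study. If the interval starts there, 56 days are added and the figures are 30.4/98 = 0.31 against 30.4/141 = 0.22, in the same direction.

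A simulation used 67 subjects, 169 days, a 10% admission risk at constant hazard, and follow-up ending 2 days after admission. It gave:

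- pooled rate (events over person-time): 0.019 per month;
- rate under full follow-up: 0.019 if the readmission hazard is unchanged, 0.022 if it is four-fold;
- mean of subject-level monthly rates: about 0.083.

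So the pooled rate is about right or slightly low, while the subject-level mean is inflated.

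**What remains missing.** Hospitalization is an SAE criterion (Section 12.1.2). SAEs are reportable to 30 days after the last dose and are followed to resolution or stabilization (Section 12.4.1). Nothing links these records to HCRU, and resolution of an event is not the same as discharge. An ER or office visit without admission is not in itself an SAE criterion, so after ET it may not be recorded anywhere as utilization.

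**The case against.** **The 48-hour cut is a worst case.** This stands in part. Section 7.1 makes 48 hours a target, and discontinuation follows the non-allowed medication, not the admission. Lorazepam is allowed (Section 10.3.3), so dosing may continue into a stay; the c = 9 columns show how much less is then lost. Against this, Section 10.3.1 allows psychotropics after the last dose only once the final PANSS is done. That PANSS belongs to the ET visit, which pulls ET toward the start of treatment for the relapse.

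**The information is not lost, and derivation rules belong in the SAP.** Admissions are captured as SAEs, and a rule linking SAE dates to HCRU could sit in an SAP that is not shown. But the collection schedule is fixed in the protocol, and an SAP cannot recover ER and office visits that were never asked about.

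**Ending HCRU with treatment is defensible.** The objective concerns the effect of the drug, and PANSS, PSP, SF-12 and MSQ also end at EOT/ET. Use after the last dose may reflect a new antipsychotic. This is a good reason to report such use separately. It does not justify counting a stay that began on treatment as shorter than it was.

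**Other stays are cut as well.** A stay of any cause open at Week 24, or one leading to discontinuation for another adverse event, is shortened in the same way. That is correct, so the fix should cover every open stay.

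**A stronger reading.** A reader might infer that the whole HCRU objective is biased downward in favour of SEP-363856. The documents do not support this. The triggering admission is counted, monthly rates can move either way, and employment status and caregiver hours are not subject to the length-of-stay truncation.

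**Conclusion.** The point holds for average length of stay and total hospital days, which are biased downward for subjects whose stay is still open at ET or Week 24. ER visits and admissions between ET and Visit 8E are also missed as HCRU. With the last dose on the admission day, ET at 48 hours and assumed mean stays of 5 to 21 days, 33% down to 9% of the true mean stay is recorded. The loss shrinks if ET is later or dosing continues after admission. The downward direction for open stays does not depend on the assumed lengths; the size does.

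For hospitalizations per month the direction is not fixed and depends on how the rate is computed. HCRU is a descriptive, single-arm endpoint in the other category, and the primary AE/SAE endpoint is unaffected. The correction is still worth making, because average length of stay would be hard to interpret for the subjects in whom it matters most.

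**What to change.** 1. In Sections 11.4.8 and 15.3.5.1, obtain admission and discharge dates for any stay open at ET or Week 24, from SAE follow-up confirmed with the site, and count the stay at full length. This is the essential step: HCRU at Visit 8E alone would still capture only 83% down to 35% of the mean stay under the assumptions above.
2. Add HCRU since last assessment to Visit 8E in Table 2 and Section 11.6.9, by telephone if needed (telephone contact is already allowed there for other items). Report use after the last dose separately from on-treatment use.
3. In Section 15.3.5.1, compute monthly counts as events over person-time, so that short ET intervals do not distort them.
4. Reconcile Section 13.1, where stopping drug ends study participation, with Section 17.3, which says that stopping medication does not necessarily end the expectation of continued participation.

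None of this alters the discontinuation rule or the timing of ET. The cost is a few minutes per subject, some programming, and a less favourable length-of-stay figure.
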